#### **Evaluating and reporting:**

The WILMA Trial Manager and the Chief Investigator and the clinical member of the team ([name]) will assess the nature of the SAE for causality and expectedness. Following the initial report, follow up data may be requested by the WILMA Trial Manager. Where the SAE and is both related and unexpected, the WILMA Trial Manager will notify the Chair of the TSC and the main REC within 15 days of receiving notification of the SAE. All SAEs will be recorded and reported annually to the main REC. A standard template will be used to record SAEs.

#### Risk of harm

MI counsellors will also be asked to notify the study team directly should they be concerned at any time that a participant has, or is likely to cause significant harm to themselves: the study team will then inform the participant's GP. MI counsellors will be asked to inform the appropriate authorities directly should they become concerned at any time that a participant has, or is likely to cause significant harm to others.

#### 10 Statistical considerations

#### 10.1 Randomisation

Allocation to groups will be by remote telephone randomisation and stratified by region (Primary Care Trust) and minimized by age, gender, ethnicity, source of recruitment (exercise referral scheme, community, etc), % weight loss and current BMI. Whoever is recruiting the potential participants will call the randomisation telephone number and the participant will be given an information pack detailing the next steps.

#### 10.2 Sample size

The sample size for the original study was 950 and based on detecting an effect size of 0.309 with 90% power at a significance level of 5%. Since this is now a feasibility study, the planned sample size will not be derived statistically. Instead the intended sample size is the number of participants it is possible to recruit based on our inclusion criteria over an 18 month period. Since recruitment has now closed our potential sample size is 170. This sample size allows us to estimate a percentage of 50% (the percentage with the greatest associated variability) to within 7.5 percentage points either side for the whole sample (n= 170), or to within 15.7 percentage points for percentages within each study arm (n = 39). These are the precisions that will be achievable for the estimation of the retention rate or any other proportion. As a feasibility study we are not primarily concerned with effectiveness, however we still feel it is informative to present the power we will have to detect differences. With our current sample size (n=170) and assuming 30% attrition, we have 39 in each of the three treatment arms. We will be able to detect a difference of 3.537 BMI points at the 5% significance level with 80% power between any two arms (our primary comparison was between the control group and the intensive arm). This is just over a difference of 9.75kgs between groups.

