#### Outcome measures

The feasibility outcomes will be measured using percentages of participants who accepted and complied with the intervention. Numbers recruited and retained will also be presented, as well as data on intervention fidelity. The primary effectiveness outcome is BMI at 1 year post randomisation and the primary contrast will be between the intensive and control groups. Secondary effectiveness outcomes include waist circumference; waist to hip ratio; self report physical activity; proportion maintaining weight loss; self report dietary intake; health related quality of life; health service and weight control resource usage; binge eating, psychological well being and duration of participation and drop out from intervention.

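### Section 10.2 claims one pair of precisions for retention and every other proportion, but one figure is taken before attrition and the other after it, so no single kind of proportion fits both

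*Protocol*

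**What the plan says.** Protocol section 10.2 takes the number recruited as fixed: "Since recruitment has now closed our potential sample size is 170". It states precision at the least favourable percentage, "This sample size allows us to estimate a percentage of 50% (the percentage with the greatest associated variability"), and gives two half-widths. The first is "to within 7.5 percentage points either side for the whole sample (n= 170"). The second is "to within 15.7 percentage points for percentages within each study arm (n = 39").

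The next sentence sets their scope: "These are the precisions that will be achievable for the estimation of the retention rate or any other proportion".

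The source of the 39 appears a little later in the same section: "With our current sample size (n=170) and assuming 30% attrition, we have 39 in each of the three treatment arms". Section 6.5 gives the same figure of about 30% for expected loss to follow-up.

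The summary of outcome measures in section 1.3 shows which proportions matter most: "The feasibility outcomes will be measured using percentages of participants who accepted and complied with the intervention". It adds the numbers recruited and retained. The proportion maintaining weight loss is listed there among the secondary effectiveness outcomes, and Table 1 in section 8.1 schedules it at 12 months.

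**The concern.** The two figures come from different populations. The whole-sample figure counts everyone recruited, and the per-arm figure counts only those expected to remain after attrition. Section 10.2 applies both to every proportion and names retention explicitly.

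For retention within an arm, the 39 cannot be the denominator. They are the expected numerator: a retention rate calculated only among those retained is 100% by construction. For a proportion that needs a 12-month measurement, the 170 cannot be the denominator unless values are supplied for those lost.

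Recruitment, retention, compliance and acceptability are the main outcomes of this feasibility study, and these two half-widths are the protocol's only stated precision for them. Someone planning the larger trial from this sentence would expect too little of per-arm retention and too much of whole-sample proportions observed at 12 months.

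**Working it through.** **Inputs**
- Total recruited: 170 (section 10.2).
- Percentage used for precision: 50% (section 10.2).
- Attrition: 30% (sections 6.5 and 10.2), so expected retention is 70%.
- Three arms (section 4). Equal allocation is an assumption; it is implied by the equal 39 per arm but not stated.
- Confidence level: 95% two-sided. This is not stated for the precisions and is assumed, but it reproduces both figures.

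**Formula**

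Half-width = 1.96 × √(p(1 − p)/n).

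**Reproducing the protocol's figures (p = 0.5)**
- n = 170: 1.96 × √(0.25/170) = 7.52 points (stated 7.5).
- n = 39: 1.96 × √(0.25/39) = 15.69 points (stated 15.7).

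Other common formulas do not reproduce the pair: a continuity correction gives 7.81 and 16.97, a t quantile 7.57 and 16.21, and the Wilson interval 7.43 and 14.97. The protocol used the simple formula above and applied it correctly.

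**Where each n comes from**
- 170 is everyone recruited, with no attrition removed.
- 170 × 0.7 = 119 followed up; 119/3 = 39.7, truncated to 39 per arm.
- 170/3 = 56.7, about 57 randomised per arm.

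**Half-widths with the matching denominator**

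| Proportion | Denominator | n | Half-width | Stated |
|---|---|---|---|---|
| Retention, overall, p = 0.5 | randomised | 170 | 7.5 | 7.5 |
| Retention, per arm, p = 0.5 | randomised | 57 | 13.0 | 15.7 |
| Retention, overall, p = 0.7 | randomised | 170 | 6.9 | – |
| Retention, per arm, p = 0.7 | randomised | 57 | 11.9 | – |
| Observed at 12 months, overall, p = 0.5 | followed up | 119 | 9.0 | 7.5 |
| Observed at 12 months, per arm, p = 0.5 | followed up | 39 | 15.7 | 15.7 |

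Rounding of n makes little difference: 56 per arm gives 13.1, and 3 × 39 = 117 overall gives 9.1.

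**Size of the mismatch**
- Retention per arm: 15.7/13.0 = 1.21, so the stated figure is about 21% too wide. Against 11.9 it is 15.7/11.9 = 1.32, about 32% too wide.
- Whole-sample 12-month proportions: 7.52/8.98 = 0.84, so the stated figure is about 16% too narrow.

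Each stated figure is right in one row and wrong in another. Neither retention nor 12-month proportions match both.

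**The case against.** The strongest reply is that nothing has been miscalculated. Both half-widths reproduce, each n is printed beside its figure, and the section says where 39 comes from. That stands: the fault lies in the scope of one sentence, not in the arithmetic.

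Several further points reduce the weight of the concern.
- The 7.5 is correct for overall retention, the one proportion the sentence names. The 15.7 is correct for per-arm proportions among people seen at 12 months.
- The error on per-arm retention is on the safe side, and 50% is openly presented as the worst case.
- The optimistic error falls mainly on secondary proportions such as weight-loss maintenance. Those are compared between arms, where the per-arm figure is the relevant one.
- Attendance and telephone contact are monitored during delivery (section 9, participant adherence), so they do not depend on completing the 12-month assessment.
- The sensitivity analysis in section 11.1 assigns previous BMI to everyone lost, which would restore the full denominator for weight maintenance. It is not the main analysis, so it does not rescue the 7.5 for proportions among those observed.
- No progression threshold, stopping rule or target is tied to these widths, and reported intervals can use the observed denominators.

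These points bear on how serious the matter is. They do not make the blanket sentence true.

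A reader might also infer a precision for MI compliance by pooling the two MI arms: 170 × 2/3 is about 113 people, giving ±9.2. The protocol does not support that as an achievable precision. It announces no such pooled proportion, the two arms have different contact schedules (section 7), and the simple formula ignores the clustering within therapist that section 11.1 allows for.

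**Conclusion.** The concern holds in a limited form. Section 10.2 pairs a pre-attrition whole-sample precision with a post-attrition per-arm precision and claims both for retention and all other proportions. Per-arm retention would be known to about ±13.0 points (±11.9 at 70% retention), better than the stated 15.7. Whole-sample proportions among those observed at 12 months would be known to about ±9.0, worse than the stated 7.5.

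These values assume equal allocation, 30% attrition spread evenly over the arms, a 95% level and the simple binomial formula without allowance for clustering.

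A reader might go further and infer that the justification for 170 participants falls with this sentence. It does not. Section 10.2 says the size was not derived statistically and is the number that could be recruited, so precision is reported after the fact. The sample size, allocation and analysis are unaffected. This is a minor to moderate correction of a stated figure, not something that must be resolved before the trial can proceed.

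**What to change.** In section 10.2, delete the sentence that extends the two figures to retention and every other proportion, and state precision by denominator (95% level, at 50%):

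- Retention, as a proportion of those randomised: ±7.5 points overall (n = 170) and ±13.0 per arm (n about 57). The values at the assumed 70% retention, ±6.9 and ±11.9, can be added.
- Proportions observed at 12 months: ±9.0 points overall (n about 119) and ±15.7 per arm (n = 39).
- MI compliance, if a precision is wanted: per MI arm on those randomised, about ±13.0, labelled as unadjusted for therapist clustering.

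State the 95% level and the equal-allocation assumption alongside. The cost is the rewording of two sentences; no design, sample size or analysis changes.

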#### 11 Analysis

#### 11.1 Main analysis

The main outcomes relate to the feasibility of the study. Descriptive statistics relating to the patient recruitment, compliance and retention and well as intervention delivery will be presented.

Given the recruitment issues it is unlikely that we will find a significant difference unless the impact of this intervention is far greater than other types of intervention in this group. So the main analyses will be completed for the study as a feasibility study. We will also examine the point estimates of effectiveness and their confidence intervals for BMI. We

will analyse for key secondary outcomes that are more immediate targets of the intervention (e.g. self-efficacy) to consider the potential of the intervention, as well as assessing if there is a trend from no intervention to the intensive intervention with the less intensive intervention lying between the two. We will undertake mediator analysis to see if the identified pathways to effect measured at six months are associated with maintenance at one year.

An intention to treat analysis will compare the three groups on average BMI using a two level linear regression model to account for clustering within therapist. The main analysis will examine the longest end-point. A secondary analysis will examine the three groups using the interim time point as the end-point. Baseline BMI and previous weight loss will be included as covariates. Both of the intervention groups will be compared to the control in this model. If there is no evidence of clustering, then this will be reduced to a one level model. Secondary outcomes will be analysed similarly using either linear (e.g. diet, waist circumference) or logistic (e.g. probability of return to previous BMI) regression.

Exploratory analysis will consider the impact of demographic factors as well as original weight loss method and theoretical moderators on the intervention effect using interaction terms included in the main analysis models. Exploratory longitudinal analysis will be undertaken to explore the effect of theoretical mediators on subsequent outcomes and interactions with the intervention groups. Individuals lost to follow-up will be compared to those who complete follow up to identify any potential biases.

A sensitivity analysis will be conducted where it will be assumed that all of those lost to follow-up returned to weight levels prior to weight loss (i.e. not baseline, but previous BMI). A Complier Adjusted Casual Effect (CACE) will also be estimated using multi-level mixture analysis. This modelling focuses on estimating the effect of the interventions in the presence of non-compliance, but also incorporates adjustments for loss to follow-up associated with the intervention. CACE approaches have been used in a number of studies of psychological therapies, using either relatively simple corrections through to the more complex multi-level mixture models proposed here. This provides a framework within which to model missingness rather than assuming missing at random (MAR).

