# 8 Study/trial outcomes

#### 8.1 Measures/assessment instruments

Measures at all outcome points will be collected face to face except the 6 month assessment which will be a postal questionnaire. Outcome measures are self-report with the exception of weight, waist and hip measurements which will be objectively measured by the researcher at each visit (N.B. the 6-month assessment comprises self-report measures only). Most of the data, apart from the moderators data (see Table 2) will be collected at baseline and post-intervention. Quality of life, physical activity and dietary data will be collected by questionnaire at 6 months during the intervention. We will also collect resource usage data at this point, since people have difficulty recalling resource use over extended periods of time and we want to be able to identify if individuals treat this as an additional intervention or a substitute e.g. for a slimming club.

With regard to cardiovascular disease, a greater BMI adds to risk prediction beyond traditional risk factor measurements.  Visceral fat is independently associated with all-cause mortality  and many of the risk factors for CVD, including type 2 diabetes mellitus.  As the direct measurement of visceral fat relies on sophisticated imaging technology, most large-scale, community-based studies have relied on anthropometric measurements of the waist and hip circumferences to determine abdominal obesity. Whilst the findings of these studies are not completely consistent, evidence suggests that a measurement of abdominal obesity (waist circumference or waist-to-hip ratio) provides explanatory information in addition to that provided by BMI. 

We will therefore measure waist and hip circumferences to assess abdominal obesity. Duplicate measurements of waist and hip circumference will be performed in accordance with standardized procedures.

Table 1 - Outcome Measures

(B=baseline; 6=6 month assessment; 12m = 12 month assessment)

| (2 0 0 0 0 0 0 0 0 0 0 0 0 0 0 0 0 0 0 0 |                    |            |           |  |
|------------------------------------------|--------------------|------------|-----------|--|
| Outcomes                                 | Measure            | When       | Time to   |  |
|                                          |                    |            | complete  |  |

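### The section 11.1 model leaves out five of the seven factors used to balance allocation, and should say that continuous secondary outcomes are adjusted for their own baseline

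*Protocol*

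**What the plan says.** **Allocation (Protocol 10.1).** Randomisation is "stratified by region (Primary Care Trust") and "minimized by age, gender, ethnicity, source of recruitment (exercise referral scheme, community, etc), % weight loss and current BMI". That makes seven balancing factors.

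**Main model (Protocol 11.1).** BMI is compared across the arms with a "two level linear regression model to account for clustering within therapist", reduced to one level if there is no evidence of clustering. On covariates the section says "Baseline BMI and previous weight loss will be included as covariates". Taking previous weight loss to be the percentage loss used in the minimisation, these are two of the seven factors. Demographic factors appear elsewhere in 11.1 only as exploratory interaction terms, and some of them return as subgroup factors in 11.2.

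**Secondary outcomes (Protocol 11.1).** "Secondary outcomes will be analysed similarly using either linear (e.g. diet, waist circumference) or logistic (e.g. probability of return to previous BMI) regression". Covariates are not listed outcome by outcome. Section 8.1 says most data "will be collected at baseline and post-intervention", and Table 1 shows baseline values for waist, hip, IPAQ, DINE, EQ-5D, EDE-Q and GHQ-12.

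**The concern.** The protocol states a covariate set, and that set does not follow the allocation scheme. Balancing arms on a prognostic factor reduces the true sampling variance of the treatment difference. A linear model without that factor cannot see the reduction: the factor's variance stays in the residual, the reported standard error is too large, and a nominal 5% test rejects less often than 5%.

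Section 8.2 gives some reason to think the omitted factors matter. It reports that older participants have done better in maintenance programmes and that ethnicity has been linked with maintenance.

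At stake is the width of the BMI interval. The protocol intends to present it with about 39 completers per arm, as an indication of effect size for a larger trial.

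The word used for the secondary outcomes raises a related question. In the BMI model, baseline BMI is the outcome's own baseline. It is not clear whether a waist or diet model would carry forward baseline BMI or the baseline of waist or diet.

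**Working it through.** **1. The plan's own figures (10.2).** 170 × 0.7 / 3 = 39.7, so 39 per arm is reproduced. That gives 3 × 39 = 117 analysed, or 170 × 0.7 = 119 before rounding. The detectable difference of 3.537 BMI points has no stated SD. Solving back with a two-sample t test (39 per arm, two-sided 5%, 80% power) gives an SD of 5.50, and an SD of 5.5 returns 3.534. The figure is plausible but cannot be verified.

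**2. Assumption.** Let R² be the share of residual variance, after baseline BMI and previous weight loss, explained by the five omitted factors. The protocol gives no value, so a range is used. The calculations ignore clustering by therapist.

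**3. Main model before any cost.** The ratio of standard errors, factors omitted to factors included, is 1/√(1 − R²):

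| R² | Ratio |
|---|---|
| 0.02 | 1.01 |
| 0.05 | 1.03 |
| 0.10 | 1.05 |
| 0.20 | 1.12 |

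**4. Cost of the extra terms.** Age 1, gender 1, ethnicity in two levels 1, source in three or four levels 2-3, and region in three areas 2, giving 7-8 degrees of freedom. Two ways of charging this were used.

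- *R² as the in-sample share.* With 117 analysed, the current model has 117 − 1 − 2 − 2 = 112 residual degrees of freedom. The ratio becomes √[(112 − k) / (112 × (1 − R²))]:

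| R² | k = 5 | k = 8 | k = 12 |
|---|---|---|---|
| 0.05 | 1.00 | 0.99 | 0.97 |
| 0.10 | 1.03 | 1.02 | 1.00 |
| 0.20 | 1.09 | 1.08 | 1.06 |

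- *R² as the true share.* A simulation minimised 170 participants to three arms on the five factors (assumed frequencies), lost 30% at random and fitted 8 extra terms. When the factors explained nothing, adding them widened the interval by 1.6%. Dividing step 3 by 1.016 gives 1.026/1.016 = 1.01 at R² = 0.05, 1.054/1.016 = 1.04 at 0.10 and 1.118/1.016 = 1.10 at 0.20. Direct simulation agrees.

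Net excess width is therefore about 0-5% at R² of 0.05-0.10. For scale, with SD 5.5 and no baseline adjustment the half-width is 1.96 × 5.5 × √(2/39) = 2.44 BMI points, and 5% of that is 0.12. The adjusted interval is narrower, so the loss is smaller still.

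**5. Size of the test.** With perfect balance among those analysed, size is 2 × [1 − Φ(1.96/√(1 − R²))]: 4.4% at R² = 0.05 and 3.9% at 0.10. Random loss of 30% restores about 30% of the chance imbalance, so 1 − R² becomes 1 − 0.7R²: 4.6% and 4.2%.

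**6. Continuous secondary outcomes.** If the model carried only baseline BMI, and this explained none of the outcome, adding the outcome's own baseline at correlation r multiplies the standard error by √(1 − r²). That is 0.87 at r = 0.5 (a 13% cut) and 0.60 at r = 0.8 (a 40% cut). For waist the gain is smaller, because baseline BMI already carries part of the information.

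**7. Logistic outcomes.** In a simulation with 117 participants, a true log odds ratio of −0.8 and a covariate log odds ratio of 1.0 per SD, the standard error was 0.469 with the covariate omitted and 0.525 with it included. The treatment log odds ratio moved from −0.82 (included) to −0.68 (omitted). Omission pulls the odds ratio towards no effect; it does not enlarge the standard error.

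**The case against.** The strongest reply is that the gain is small and rests on an assumption. Baseline BMI is already in the model and is probably the strongest predictor. Section 8.2 is guarded about the rest: several studies found no differential effect by gender, the effect of age is described as unclear, and the ethnicity finding may be confounded. At R² of 0.05 or less, the degrees of freedom can cancel the gain. Section 10.2 says effectiveness is not the main concern, and 11.1 expects no significant difference. All of this stands, and it sets the weight of the point. It does not remove the mismatch between 10.1 and 11.1, and a fitted model that follows the allocation costs little.

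It can also be said that allocation was stratified by Primary Care Trust, so three broad areas are not the actual stratifier. That is true. With about 117 analysed, the collapse is a compromise between following the design and saving degrees of freedom.

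A reader might infer that the secondary outcomes will be analysed without their own baseline. The text does not say so. Because baseline BMI is the own baseline in the BMI model, analysing other outcomes in a similar way can equally mean using theirs, and covariate lists by outcome are commonly left to the SAP. This part is a request to make the wording explicit. The 13-40% applies only under the literal reading.

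**Conclusion.** The point holds as a minor improvement in precision. The stated BMI model omits region, age, gender, ethnicity and source of recruitment, all used in allocation. For linear outcomes this makes intervals about 0-5% too wide net of degrees of freedom if those factors explain 5-10% of residual variance, and more (6-10% at R² of 0.20) if they explain more. The nominal 5% test then runs at roughly 4-5% after the assumed attrition. These figures depend on an assumed R², on loss at random and on negligible clustering.

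Three stronger readings are not supported:
- The treatment estimate is not biased by the omission in the linear model; the error is on the conservative side.
- The standard-error argument does not cover the logistic outcomes, where the effect is attenuation of the odds ratio.
- Own-baseline adjustment cannot be asked of return to previous BMI or of the proportion maintaining weight loss, which have no baseline value.

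**What to change.** In section 11.1:

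1. Add the remaining balancing factors to the BMI model alongside baseline BMI and previous weight loss: age, gender, ethnicity, source of recruitment and region. Collapse sparse levels before the outcome data are seen, for example ethnicity to two levels, source to three or four, and region to Wales, South West England and East Midlands. If any factor is left out, give the reason.
2. State that each continuous secondary outcome measured at baseline (waist, hip, IPAQ, DINE, EQ-5D, EDE-Q, GHQ-12) is adjusted for its own baseline value, with the same balancing factors.
3. State that return to previous BMI and the proportion maintaining weight loss keep baseline BMI and previous weight loss as covariates, since neither has a baseline of its own.

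The cost is two or three sentences and about 7-8 degrees of freedom out of 117-119 analysed. No new data are needed, because the factors are already recorded for allocation.

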# 4 Study/trial design

This is a feasibility study of a three arm individually randomised controlled trial. The three arms are: an intensive intervention arm, a less intensive intervention arm and a control arm that will receive an information pack and usual care (the intervention arms will also receive the information pack). The two experimental arms will receive a 12 month intervention, which will differ with respect to how intensive the intervention is in terms of the amount of contact with the MI therapist. Individuals will be followed up at 6 months during the intervention and at around 12 months – after the intervention has been delivered (one year from randomisation). Obese adults aged 18-70 with a current or previous BMI of 30+ who have lost a minimum of 5% body weight during the previous twelve months will be recruited.

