#### 7 Study/trial intervention

#### Intensive Intervention Group:

Participants in this group will have 6 one-to-one individually tailored MI sessions. The sessions will be delivered by experienced MI counsellors who will have their skills assessed prior to being employed by the study team. These sessions will be delivered fortnightly for three months and will last approximately 60 minutes. A systematic review of MI as an intervention found an effect in 87% of studies with more than five encounters the versus only 40% with one session of MI. For the final nine months of the intervention participants will have monthly MI telephone calls lasting around 20 minutes. This level of monthly contact in the intensive intervention group is based on previous trials. Telephone support has been shown to be effective in weight loss interventions and provides a clear cost advantage over face-to-face sessions. Key aspects of MI will be used including reflective listening, developing discrepancy, participant directed goal setting and consideration of how to implement these, information giving, identification of barriers and supporting participants' self efficacy.

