# Control Group:

sessions.

The control group will be given an information pack detailing lifestyle changes for weight maintenance (the intervention groups will also receive this). The content of the information pack is based on useful resources for weight loss and healthy lifestyle, and advice from a user representative, dietician and physical activity specialist specifically on weight maintenance.

All participants in all groups will still be able to access usual care. They may continue, for example to attend a weight loss group and may still be attempting to lose more weight. Participants in both intervention groups will be given the same information pack as the control group with guidance on diet and physical activity. The MI sessions will be held locally to participants. Sessions will be held in suitable rooms, e.g. small meetings rooms in

hotels community centres. Participants will also be offered the MI sessions at home if they prefer.

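### The rule to drop the therapist level when clustering is not evident is a low-power pre-test that can make the BMI intervals somewhat too narrow

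*Protocol*

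**What the plan says.** Section 11.1 compares the three arms on average BMI by intention to treat, with a "two level linear regression model to account for clustering within therapist". The contrasts come from that same fit: "Both of the intervention groups will be compared to the control in this model". The next instruction makes the model depend on the data: "If there is no evidence of clustering, then this will be reduced to a one level model". No test, threshold or ICC cut-off defines what counts as evidence. Secondary outcomes are to be handled in the same way, so the rule reaches them too.

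Only two arms have a therapist. Section 4 describes the experimental arms as ones "which will differ with respect to how intensive the intervention is in terms of the amount of contact with the MI therapist". In section 7 the intensive arm is told: "Participants in this group will have 6 one-to-one individually tailored MI sessions". The less intensive arm has two face-to-face sessions and two calls. For controls, "The control group will be given an information pack detailing lifestyle changes for weight maintenance".

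Section 11.1 makes feasibility the main outcome but still promises point estimates and confidence intervals for BMI. Sections 1.3 and 3.1 say that these results should indicate effect sizes for a larger trial.

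**The concern.** The reduction rule treats failure to detect clustering as if clustering were absent. That is reasonable only when the check has good power. Here the therapist variance is estimated from about 78 treated participants spread over an unstated number of counsellors, so power is poor.

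When real clustering is missed, the one-level model treats patients of the same counsellor as independent. The standard error of intervention versus control is then too small and the interval too narrow. Because the choice follows a look at the estimated clustering, the reported interval also ignores the uncertainty of that choice.

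At stake is the precision claimed for the primary effectiveness contrast, intensive versus control. A later trial planned from an over-precise interval inherits the error.

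**Working it through.** **1. The plan's own figures (section 10.2).**
- Analysed per arm: 170 × 0.70 / 3 = 39.7, stated as 39. This reproduces.
- Detectable difference: 3.537 BMI points at 5% significance and 80% power. No SD is given, so it can only be solved backwards. Under the normal approximation, 3.537 / [(1.960 + 0.842) × √(2/39)] = 3.537 / 0.634 = 5.575. Under the t distribution, 3.537 / 0.6426 = 5.50. The figure is consistent with independent observations and an SD near 5.5. Section 10.2 does not mention therapist clustering.

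**2. Assumed inputs.** The number of therapists *k* and the ICC *ρ* are not in the protocol. I take *k* = 4 to 10 and *ρ* = 0.02 to 0.10, with patients spread evenly over therapists and equal total variance in every arm.

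**3. How far the one-level standard error falls short.** With *m* = 39/*k* patients per therapist in an arm and unclustered controls, the ratio of true to one-level standard error is

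R = √{[2 + (m − 1)ρ] / 2}.

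The type I error of a nominal 5% one-level test is 2[1 − Φ(1.96/R)]. The detectable difference becomes 3.537 × R.

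Central case, *k* = 6 and *ρ* = 0.05: m = 6.5, (m − 1)ρ = 0.275, R = √(2.275/2) = 1.067.

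| k | ICC | R | One-level type I error | Detectable difference | Power at 3.537 |
|---|---|---|---|---|---|
| 4 | 0.02 | 1.043 | 6.0% | 3.688 | 76.6% |
| 4 | 0.05 | 1.104 | 7.6% | 3.905 | 71.8% |
| 4 | 0.10 | 1.199 | 10.2% | 4.241 | 64.7% |
| 6 | 0.02 | 1.027 | 5.6% | 3.633 | 77.9% |
| 6 | 0.05 | 1.067 | 6.6% | 3.772 | 74.8% |
| 6 | 0.10 | 1.129 | 8.3% | 3.994 | 69.9% |
| 10 | 0.02 | 1.014 | 5.3% | 3.588 | 78.9% |
| 10 | 0.05 | 1.036 | 5.8% | 3.663 | 77.2% |
| 10 | 0.10 | 1.070 | 6.7% | 3.785 | 74.5% |

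The true standard error is thus 1.4% to 19.9% above the one-level value.

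**4. What the rule does.** The protocol names no test, so the simulation used a likelihood-ratio statistic above 2.706. It ran 4,000 null trials per scenario with 39 per arm, therapists working in both active arms, and independent controls.

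| k | ICC | Clustering detected | Type I: always one level | Type I: rule followed | Type I: therapist effect kept |
|---|---|---|---|---|---|
| 6 | 0.02 | 9% | 5.3% | 5.1% | 4.9% |
| 6 | 0.05 | 19% | 6.5% | 6.0% | 5.3% |
| 6 | 0.10 | 39% | 8.8% | 7.1% | 6.4% |
| 10 | 0.02 | 8% | 6.1% | 5.9% | 5.8% |
| 10 | 0.05 | 15% | 6.1% | 5.6% | 5.4% |
| 10 | 0.10 | 33% | 6.5% | 5.8% | 5.5% |

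The Monte Carlo standard error near 5% is √(0.05 × 0.95 / 4000) = 0.34 percentage points, so the small gaps at *k* = 10 should not be over-read.

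A separate simulation over *k* = 4 to 10 and ICC 0.02 to 0.10 detected clustering in 9% to 47% of trials. Type I error was 5.5% to 10.5% at one level, 5.1% to 6.4% with the rule, and 3.5% to 4.5% with clustering kept. Taken together, real clustering is missed in about 53% to 92% of trials. The runs differ on whether the retained model is slightly liberal or slightly conservative. The first used a normal reference for it, and with few therapists that choice matters.

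**The case against.** The strongest reply is that little rests on this. Section 10.2 says that effectiveness is not the primary concern, section 11.1 expects no significant difference, and no decision hangs on the BMI test. Point estimates barely move. In the central case the standard error is about 7% too small and the rule costs about 0.7 percentage points of type I error (6.0% against 5.3%). This stands, and it limits the severity.

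It is also fair that the number of therapists may not be small. Recruitment covers Wales, South West England and the East Midlands, sessions are held locally, and two counsellor focus groups are planned. More therapists would shrink the effect. It would be too strong to say that the check nearly always fails: at an ICC of 0.10 it succeeds in a third or more of the simulated trials at *k* = 6 and *k* = 10.

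A reader might infer a second error: that the model needs a therapist for controls, who have none, and so ties the treatment contrast to a single control cluster. The protocol does not say this. A model with a therapist effect in the treated arms only is itself a two-level model and fits the wording, and the coding of controls could be settled in an analysis plan that is not shown. The coding also matters less than it seems. At *k* = 6 and ICC 0.05 / 0.10, controls entered as single-person clusters gave type I error of 5.1% / 6.3%, against 5.3% / 6.4% with the therapist effect confined to the active arms. Only the one-cluster coding was clearly off (3.1% / 2.9%, too conservative).

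A reader might also infer that the ICC will go unreported. Nothing in section 11.1 prevents its being reported.

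The reduction sentence itself remains. It is a positive instruction, and an analysis plan could define its threshold but could not remove it without departing from the protocol.

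**Conclusion.** The point holds for the reduction rule. Under 4 to 10 therapists and an ICC of 0.02 to 0.10, both assumed, the rule discards real clustering in roughly half to nine-tenths of trials. The BMI intervals for intervention versus control can then be somewhat too narrow: the true standard error is about 1% to 20% above the one-level value. Type I error is about 5% to 7% when the rule is followed, and up to about 10% if every trial were analysed at one level. With an ICC of 0.02 or less, or many therapists, the effect is negligible.

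Recruitment, retention, compliance and delivery results are unaffected. The harm is confined to the BMI intervals, the secondary outcomes analysed in the same way, and the effect-size information passed to a larger trial. The documents do not support reading this as invalidating the primary comparison or as an error in how controls are modelled. Severity is minor to moderate.

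**What to change.** In section 11.1:

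- Delete the sentence that reduces the model to one level.
- State that the therapist random effect applies to the two intervention arms only, with controls treated as unclustered, and is kept whatever its estimate.
- Name a small-sample degrees-of-freedom method, such as Satterthwaite or Kenward-Roger.
- Report the therapist ICC with its interval, since a larger trial would need it.

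This changes wording only and needs no new data. It should be settled before the estimated clustering is seen. The cost is slightly wider, mildly conservative intervals if true clustering is negligible.
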